#### **3.1 Study Design and Duration**

This is a Phase 1/2a, open-label study to characterize the safety and tolerability, as well as preliminary efficacy, PK, and PD of BMS-986148 administered alone and in combination with nivolumab in subjects with select advanced solid tumors (pancreatic, ovarian, NSCLC, gastric, or mesothelioma). The study has 3 segments: Part 1 (Phase 1 study - dose escalation), Part 2 (Phase 2a - dose expansion), and Part 3 (BMS-986148 in combination with nivolumab; Part 3A - dose escalation and Part 3B - dose expansion) (see [Figure 3.1-1](#)). All subjects will complete up to 4 study periods: Screening (up to 28 days), Treatment (21 days/cycle Q3W or 28 days/cycle QW), Follow-up (60 or 100 days), and Survival Follow-up (see [Figure 3.1-2](#)). After completing the Follow-up period, subjects will continue to be followed for [REDACTED] up to 2 years from first dose

of study drug for subjects discontinuing study drug prior to 2 years. Subjects receiving study drug for more than 2 years will be followed in the Survival Follow-up period for 6 months from their last treatment date. With Amendment 3, a dose escalation phase will be conducted with BMS-986148 and nivolumab combination therapy (Part 3A). In the BMS-986148 and nivolumab combination therapy dose expansion phase (Part 3B), additional subjects with pancreatic, ovarian, NSCLC, gastric, or mesothelioma will be treated at or below the MTD of the combination dose identified in Part 3A to confirm safety and evaluate anti-tumor activity.

[figure not shown]
The duration of the study is anticipated to be approximately 5 years from the time of the first visit of the first subject to the required Survival Follow-up of the last subject enrolled. The end of the study will occur when the last subject has the last Survival Follow-up visit.

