#### **3.1.2 Dose Expansion (Part 2)**

The purpose of the cohort expansion will be to assess preliminary antitumor efficacy, expanded safety experience, and PD effects of BMS-986148. Additional subjects will be treated after the completion of Part 1A and/ or Part 1B, at the MTD, or at an alternative dose below MTD as agreed upon by the BMS Medical Monitor and investigators. Part 2 can begin before the completion of Part 1B as the Q3W dosing regimen is the intended regimen for Part 2. However, if the aggregate PK and safety data indicate similar safety but higher cumulative exposure with the QW dose schedule, this schedule may also be evaluated in Part 2 in an additional cohort of 25 to 26 subjects, once the MTD or a tolerated dose below the MTD is identified in Part 1B. Treatment doses in the cohort expansion groups will not exceed the MTD.

Five expansion cohorts will be restricted to these tumor types 1) mesothelioma 2) pancreatic 3) ovarian 4) NSCLC, and 5) gastric cancer. Enrollment in cohort expansion will be determined by the mesothelin expression of the archived tumor sample (or fresh tumor sample if archived sample is not available).

The enrollment in each expansion cohort will be guided by a Simon 2-Stage design framework (see [Table 8.1-1](#)) exploring efficacy in the following 2 populations: [REDACTED]

Anti-tumor activity will be assessed initially in approximately 12 to 15 evaluable subjects per tumor type (Stage 1) treated in each monotherapy cohort, with the option to stop enrolling in a cohort without an initial anti-tumor activity signal. The number of subjects needed for the Stage 1 review is guided by a Simon 2-Stage design as shown in Table 8.1-1 below for each tumor type with futility boundaries as follows: after Stage 1, if none of the first 15 evaluable subjects in the gastric or pancreatic cohorts, if  $\leq 2$  of the first 12 with mesothelioma, or  $\leq 1$  of the first 14 with NSCLC or ovarian cohort demonstrate clinical activity, enrollment in the cohort meeting criteria may be stopped for this population.

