**Table 5.1-1: List of Study Parts and Corresponding Study Assessments and Procedures Tables**

Part of Study	Table
1A	Table 5.1-2 , Screening and Cycle 1 Table 5.1-3 , Cycle 2 to Off Study Visit
1B	Table 5.1-4 , Screening and Cycle 1 Table 5.1-5 , Cycle 2 to Off Study Visit
2	Table 5.1-2 and Table 5.1-4 , Screening and Cycle 1 for Q3W and QW dosing, respectively Table 5.1-3 and Table 5.1-5 , Cycle 2 to Off Study Visit for Q3W and QW dosing, respectively
3A	Table 5.1-6 , Screening and Cycle 1 Combination Therapy Table 5.1-7 , Cycle 2 to Off Study Visit Combination Therapy Table 5.1-8 , Part 3 Retreatment (Part 3 subjects only)
3B	Table 5.1-6 , Screening and Cycle 1 Combination Therapy Table 5.1-7 , Cycle 2 to Off Study Visit Combination Therapy Table 5.1-8 , Part 3 Retreatment (Part 3 subjects only)

**Table 5.1-2: Screening and Cycle 1, Parts 1A and 2 (Q3W BMS-986148 Monotherapy Dosing / 21 Day Cycle) Procedural Outline (CA008002)**

Procedure a	Pre-Screening	Screening Visit D-28 to D-1	C1D1	C1D2	C1D4 b	C1D8	C1D15	Notes
Eligibility Assessments								
Informed Consent		X						A subject is considered enrolled only when a protocol specific informed consent is signed. In Part 2, if allowed by institutional practices, sites are encouraged to use a pre-screening consent for the mesothelin-expressing tumor analysis. Other screening procedures should not be done before the mesothelin-expressing tumor analysis is available for the determination of subject eligibility.
Inclusion/Exclusion Criteria		X						
ECOG		X	X					
Medical History		X						Also include any toxicities or allergy related to previous treatments. Smoking history for all subjects.
Prior Treatments		X						Including prior cancer treatment regimens and medications administered within 4 weeks of dosing.
Safety Assessments								
PE		X	X					If the screening PE is performed within 24 hours prior to dosing on Day 1, then a single exam may count as both the screening and pre-dose evaluation.  A neurological exam must be included at the screening or pre-dose at the C1D1 visit.

**Table 5.1-2: Screening and Cycle 1, Parts 1A and 2 (Q3W BMS-986148 Monotherapy Dosing / 21 Day Cycle) Procedural Outline (CA008002)**

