Ophthalmological Examination d	Start of Cycle 2, every 2 cycles thereafter, and as clinically indicated.												X			Performed by ophthalmologist or locally qualified personnel. Any abnormality must be discussed with the medical monitor prior to dosing. Ophthalmological exams can be done up to 72 hours prior to dosing.
Physical	X				X						X			X	X	Weight only.

**Table 5.1-5: Cycle 2 to Off Study Visit, Part 1B (Weekly Dosing BMS-986148 Monotherapy Dosing / 28 Day Cycle) Procedural Outline (CA008002)**

Procedure a	C2 and C3				C4				C5 and Beyond			EOT	Follow-up (30 and 60 Days After Last Dose)	Survival Follow- up b	Notes	
	D1	D8	D15	D22	D1	D2	D4 c	D8	D15	D1	D8	D15		(±5 days)		(±2 weeks)
Measurements																
Vital Signs e	X	X	X	X	X			X	X	X			X	X		See note in screening procedures.
ECGs	X				X	X		X	X	X			X	X		See note in screening procedures.
Echocardiogram	Start of Cycle 3, then every 3 cycles thereafter, and as clinically indicated.												X			On treatment echocardiogram exams may be done up to 72 hours prior to dosing.
Laboratory Tests	X	X	X	X	X		X	X	X	X			X	X		See note in screening procedures and Section 5.3.1 . Lab tests can be performed up to 24 hours prior to dosing. C4D4 (CBC only) collection to be time matched with PK collection pre-dose.

**Table 5.1-5: Cycle 2 to Off Study Visit, Part 1B (Weekly Dosing BMS-986148 Monotherapy Dosing / 28 Day Cycle) Procedural Outline (CA008002)**

Procedure a	C2 and C3				C4					C5 and Beyond			EOT	Follow-up (30 and 60 Days After Last Dose)	Survival Follow- up b	Notes
	D1	D8	D15	D22	D1	D2	D4 c	D8	D15	D1	D8	D15		(±5 days)	(±2 weeks)	
Tumor Biopsy (Fresh) Part 2 Only	X															C2D1 (±3 days). For 10 ovarian cancer subjects and 10 gastric cancer subjects who provided pre-treatment biopsies.
Pregnancy Test	X	X	X		X			X	X	X	X	X	X	X		
Concomitant Treatments	X	X	X	X	X	X	X	X	X	X	X	X	X	X f		
Adverse Event Reporting																
Monitor for Non-SAEs	X	X	X	X	X	X	X	X	X	X	X	X	X	X		See note in screening procedures.
Monitor for SAEs	X	X	X	X	X	X	X	X	X	X	X	X	X	X		See note in screening procedures.
PK and Immunogenicity Assessments (See Section 5.5)																
Efficacy Assessments																
Tumor Assessment	At the start of Cycle 3 and then every 2 cycles thereafter (±1 week).												X	X g	X h	See Sections 5.3.1 and 5.4.1.

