### **5.3 Safety Assessments**

All subjects who receive at least 1 dose of study drug will be evaluated for safety parameters. Additionally, any occurrence of an SAE from the time of consent until 60 days (or 100 days for combination therapy) post discontinuation of study drug dosing will be documented. Any occurrence of nonserious AEs will be collected from first dose of study drug until 60 days (or 100 days for combination therapy) post discontinuation of dosing.

AEs will be coded using the most current version of Medical Dictionary for Regulatory Activities and reviewed for potential significance and importance. Adverse events will be evaluated according to the NCI CTCAE v4.03. Subjects should be followed until all AEs for which no clear alternative cause is identified other than BMS-986148 have recovered to baseline or are deemed irreversible by the investigator. Safety assessments will be based on medical review of AE reports and the results of vital sign measurements, PEs, and clinical laboratory tests. The incidence of AEs will be tabulated and reviewed for potential significance and clinical importance. The schedule of required visits, tests, procedures, and assessments are described in [Table 5.1-2](#) through [Table 5.1-8](#). In limited instances, scheduled events (including events other than safety assessments) can occur outside of the indicated timeframes but the Sponsor should be notified.

Only data for the procedures and assessments specified in this protocol (see [Table 5.1-2](#) through [Table 5.1-8](#)) should be submitted to BMS. Additional procedures and assessments may be performed as part of standard of care; however, data for these assessments should remain in the subject's medical record and should not be provided to BMS unless specifically requested by the Sponsor.

If a subject has a delay in study drug administration for any reason, then assessments and laboratory tests (with the exception of any tests needed to ensure subject safety) should be correspondingly delayed with the exception of tumor assessments (ie, continue scans Q6W for Parts 1A, 2, and 3 and Q8W for Part 1B  $\pm$  1 week regardless of dosing delays).

At baseline, a medical history will be obtained to capture relevant underlying conditions. Baseline signs and symptoms are those that are assessed within 2 weeks prior to subject enrollment. Any new or worsening clinically significant changes must be reported on the appropriate nonserious or serious AE page.

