### **8.4.2 Efficacy Analyses**

Efficacy results will be presented by tumor type, dose and regimen for monotherapy and combination cohorts. Individual BOR, duration of response and PFS will be listed using RECIST version 1.1 criteria or Modified RECIST for malignant pleural mesothelioma ([Appendix 4](#)). BOR outcomes will be tabulated by dose and dose regimen. The ORR and PFS rates (eg, at 24 weeks) and the CI will be provided by dose and dose regimen for each tumor type if there is a large enough sample size. The duration of response and PFS will be estimated by Kaplan-Meier (K-M) methodology, PFS rates (eg, at 24 weeks) will be similarly estimated, based on K-M methodology. Individual changes in the tumor burden over time will be presented graphically by dose and dose regimen within a tumor type.

Sponsor can request scans for review at any time during or after the study. Sponsor can request scans for review at any time during or after the study.

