### 7.2 Grouping Scheme

Individual subject's data will be listed in the order of subject ID and collection time.

Throughout this analysis plan, a cohort is defined a unique group of subjects identified by study phase (escalation, expansion), dose, dose regimen (Q3W or QW for 3 weeks followed by one week off), and tumor type (if in expansion phase). Summary analyses in this study will be performed with various grouping schemes: cohort, dose+dose regimen, expansion cohorts only, and overall, as shown in [Table 2](#). The scheme of dose + dose regimen consists of groups decided

by the unique combination of dose and dose regimen, regardless of tumor type and study phase. The scheme of expansion cohorts only has the five groups of subjects with different tumor types enrolled into the expansion cohorts.

Grouping for efficacy analyses are further divided by different endpoints as in Table 2, where analyses of BOR and ORR will be done by cohort, and other endpoints will be summarized for expansion cohorts only by tumor type.

Safety analyses will be conducted using data from all cohorts by dose, dose regimen and overall. If appropriate, certain safety endpoints may be summarized with further grouping of tumor type.

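### If the optional Part 2 weekly cohort opens, its scan interval is inconsistent (8 weeks in Table 5.1-5, 6 weeks in Section 5.3), and the SAP's tumor-type grouping would merge it with Q3W for PFS, PFS rate and duration of response

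*Protocol*

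**What the plan says.** **The weekly cohort.** Q3W is the intended Part 2 regimen. Protocol 3.1.2 adds that, if PK and safety data support the weekly schedule, "this schedule may also be evaluated in Part 2 in an additional cohort of 25 to 26 subjects".

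**The scan calendar.** For Part 2, Table 5.1-1 names Tables 5.1-3 and 5.1-5 as covering "Cycle 2 to Off Study Visit for Q3W and QW dosing, respectively". Table 5.1-5 is titled for Part 1B but has a biopsy row marked for Part 2 only. Its tumor-assessment rule is "At the start of Cycle 3 and then every 2 cycles thereafter (±1 week". Section 5.4.1 gives the same two-cycle rule. Section 5.3 has a sentence that opens "If a subject has a delay in study drug administration for any reason" and exempts tumor assessments from the delay: "continue scans Q6W for Parts 1A, 2, and 3 and Q8W for Part 1B".

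**The endpoint.** Protocol 8.3.2.2 gives 12, 24 and 36 weeks as example times for the PFS rate and ties each to its planned scan visit. SAP 4.2.2 lists the same times without the tie to the scan.

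**The grouping.** Protocol 8.4.2: "Efficacy results will be presented by tumor type, dose and regimen for monotherapy and combination cohorts". SAP 7.2 analyses BOR and ORR by cohort, and says that "other endpoints will be summarized for expansion cohorts only by tumor type". SAP Table 2 and 7.5 follow this for PFS, PFS rate and duration of response.

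**The concern.** Section 5.3 assigns the scan interval by study part, while the procedure tables assign it by cycle length. The two agree everywhere except for a Part 2 subject on QW. A progression dated at a scan can appear only at or after a scheduled visit, so two regimens scanned on different calendars can show different PFS rates at a fixed week even when the true PFS is the same.

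Two separate things are at stake. If results are shown by regimen, the QW rates at weeks 12 and 36 would carry an upward shift from the calendar alone. If results are merged by tumor type, the reader cannot see what each regimen contributed, and the merged rate carries part of that shift. The calendar has to be settled before the cohort opens, because scans that were not made cannot be recovered.

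**Working it through.** **Inputs**
- Cycle length: "Treatment (21 days/cycle Q3W or 28 days/cycle QW" (Protocol 3.1).
- Scan rule: start of Cycle 3, then every 2 cycles, ±1 week (Tables 5.1-3 and 5.1-5).
- Times of interest: weeks 12, 24 and 36 (Protocol 8.3.2.2, SAP 4.2.2).
- Median PFS: not given in the documents. Medians of 8, 13 and 26 weeks are assumed.

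**Step 1: reproduce the stated intervals.** Interval in weeks = 2 × cycle days / 7.
- Q3W: 2 × 21 / 7 = 6. This matches Section 5.3 for Parts 1A and 3 and for Part 2 on Q3W.
- QW: 2 × 28 / 7 = 8. This matches Section 5.3 for Part 1B, but not the 6 weeks it gives for Part 2 if the subject is on QW.

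**Step 2: lay out the calendars.**
- 6-weekly: weeks 6, 12, 18, 24, 30, 36.
- 8-weekly: weeks 8, 16, 24, 32, 40.

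With ±1 week, the 8-weekly scans nearest to week 12 fall in weeks 7 to 9 and 15 to 17, and those nearest to week 36 in weeks 31 to 33 and 39 to 41. None reaches week 12 or 36. Week 24 is a scan week on both calendars. This step needs no model.

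**Step 3: illustrate the size.** Let S(t) = 0.5^(t / median), with progression seen only at scans, scans exactly on schedule, and no deaths. The observed rate at week t is then S at the last scan on or before t. At week 12 that is S(12) on the 6-week calendar and S(8) on the 8-week calendar. At week 36 it is S(36) and S(32).

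| Assumed median | Wk 12, 6-weekly | Wk 12, 8-weekly | Gap | Wk 36, 6-weekly | Wk 36, 8-weekly | Gap |
|---|---|---|---|---|---|---|
| 8 weeks | 35.4% | 50.0% | +14.6 | 4.4% | 6.3% | +1.8 |
| 13 weeks | 52.7% | 65.3% | +12.5 | 14.7% | 18.2% | +3.5 |
| 26 weeks | 72.6% | 80.8% | +8.2 | 38.3% | 42.6% | +4.3 |

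Gaps are in percentage points, from unrounded values. At week 24 both calendars read S(24), so the gap is 0.

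**Step 4: the merged rate.** If half of a tumor-type group were on QW, the merged week-12 rate would carry half the gap: 8.2 / 2 = 4.1 to 14.6 / 2 = 7.3 points. The documents do not give the tumor mix of the QW cohort, so the true share is unknown.

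**Step 5: sensitivity to slippage.** Take the 13-week median and suppose half of the scans due at the landmark fall just after it.
- Week 12: the 6-week calendar reads (S(6) + S(12)) / 2 = (0.726 + 0.527) / 2 = 0.627, against 0.653 on the 8-week calendar. The gap falls to about 2.6 points.
- Week 24: (S(18) + S(24)) / 2 = (0.383 + 0.278) / 2 = 0.331, against (S(16) + S(24)) / 2 = (0.426 + 0.278) / 2 = 0.352. The gap rises from 0 to about 2 points.

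The rates therefore need to be read after the planned scan, as Protocol 8.3.2.2 intends and SAP 4.2.2 omits.

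**Step 6: compare the groupings.** Protocol 8.4.2 splits efficacy by tumor type, dose and regimen. SAP 7.2 includes regimen in its definition of a cohort, so BOR and ORR would be split by regimen. Its expansion-cohorts-only scheme has five tumor-type groups with no regimen factor, so PFS, PFS rate and duration of response would not be.

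**The case against.** The strongest reply has five parts.

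- **Section 5.3 is not a scan schedule.** The words sit in a sentence about dosing delays, the procedure tables hold the schedule, and Section 5.4.1 agrees with them. The wording by part may be shorthand for the intended Q3W regimen. This stands: a reader might infer that Section 5.3 puts every Part 2 QW subject on 6-week scans, and it does not. An undelayed QW subject simply follows Table 5.1-5. The conflict is met by a delayed QW subject, who is told to continue at an interval never in use for that subject.
- **The QW cohort is optional, and no PFS comparison between regimens is planned.** This also stands. The protocol has no formal hypothesis, PFS is secondary, and the cohort would open on PK and safety grounds.
- **The SAP does not say that it pools.** Correct. Merging is inferred from the grouping. SAP 6.2 assumes one selected regimen for all five cohorts, so within its own scope there is nothing to merge. SAP version 1.0 describes only Parts 1 and 2. But SAP 6.2 leaves no place for the second regimen that the protocol allows, and following its grouping as written would merge the two.
- **The two harms exclude each other.** For any one table they do: it is either split or merged. Each is a problem in its own case.
- **The gap is fragile and small against sampling error.** Deaths count on their own date, scans may be made early if clinically indicated, and Step 5 shows what slippage does. With 25 subjects and a rate of 53%, the 95% half-width is 1.96 × √(0.53 × 0.47 / 25) = 0.196, about 20 points. This limits the weight of the figures. It does not remove the calendar mismatch.

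**Conclusion.** The point holds, on condition that the Part 2 QW cohort opens. Two findings rest on the text alone: Table 5.1-5 and the delay sentence in Section 5.3 give different scan intervals for that cohort, and the SAP grouping for PFS, PFS rate and duration of response omits the regimen factor that Protocol 8.4.2 requires. That an 8-week calendar has no planned scan at week 12 or 36 follows by arithmetic.

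The size is an illustration only. The week-12 gap of about 8 to 15 points and the week-36 gap of about 2 to 4 points assume exponential PFS, scans exactly on schedule, no deaths, and medians of 8 to 26 weeks. In practice the week-12 gap would be smaller.

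A reader might go further and infer that QW would look better on PFS as a whole. The documents do not support that. Week 24, the only time named in Protocol 8.4.2, is common to both calendars. The observed median can move either way: with exponential PFS, a true median of 12 weeks reads as 12 weeks on 6-weekly scans and 16 on 8-weekly scans, while a true median of 16 weeks reads as 18 and 16.

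**What to change.** 1. In SAP 7.2, Table 2 and 7.5, present PFS, PFS rate and duration of response for the expansion cohorts by tumor type and dose regimen. This brings the SAP into line with Protocol 8.4.2. It costs wording and a grouping variable in the tables.
2. Reconcile Section 5.3 with Table 5.1-5 on the scan interval for Part 2 QW subjects, with and without dosing delay, before that cohort opens. Which interval applies is for the sponsor to settle. The wording change itself costs little. The scan burden depends on the choice: through week 24 there are 24 / 6 = 4 on-treatment scans on one calendar and 24 / 8 = 3 on the other.
3. If the two regimens keep different calendars, limit any descriptive comparison of PFS rates between them to week 24. Carry into SAP 4.2.2 the clause in Protocol 8.3.2.2 that the rate is read after the planned scan. This needs no extra data.

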### **3.5 Discontinuation of Subjects following any Treatment with Study Drug**

Subjects **MUST** discontinue investigational product (and noninvestigational product at the discretion of the investigator) for any of the following reasons:

- Subject's request to stop study treatment and/or participation in the study
- Any clinical AE, laboratory abnormality, or intercurrent illness which, in the opinion of the investigator, indicates that continued participation in the study is not in the best interest of the subject
- Termination of the study by BMS
- Loss of ability to freely provide consent through imprisonment or involuntarily incarceration for treatment of either a psychiatric or physical (eg, infectious disease) illness
- Inability to comply with protocol
- Discretion of the investigator

- Confirmed CR as defined by RECIST version 1.1 or Modified RECIST for malignant pleural mesothelioma (see [Appendix 4](#)) unless subject meets criteria to continue treatment with nivolumab
- Documented disease progression as defined by RECIST version 1.1 or Modified RECIST criteria for malignant pleural mesothelioma (see [Appendix 4](#)) unless subject meets criteria for treatment beyond progression ([Section 4.5](#)) (for subjects in Part 3)
- AE(s) requiring discontinuation as outlined in the Dose Modification section (See [Section 4.5.2](#))

In the case of pregnancy, the investigator must immediately notify the BMS Medical Monitor/designee of this event. In most cases, the study drug will be permanently discontinued in an appropriate manner. If the investigator determines a possible favorable benefit/risk ratio that warrants continuation of study drug, a discussion between the investigator and the BMS Medical Monitor/designee must occur.

All subjects who discontinue investigational product should comply with protocol specified follow-up procedures as outlined in [Section 5](#). The only exception to this requirement is when a subject withdraws consent for all study procedures including post-treatment study follow-up or loses the ability to consent freely (ie, is imprisoned or involuntarily incarcerated for the treatment of either a psychiatric or physical illness).

If study drug is discontinued prior to the subject's completion of the study, the reason for the discontinuation must be documented in the subject's medical records and entered on the appropriate CRF page.

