#### **4.5.2 Guidelines for Dose Modifications**

Subjects will be monitored continuously for AEs while on study therapy. Subjects will be instructed to notify their physician immediately for any and all AEs. For the purposes of subject management, drug-related AEs occurring at any time that meet the DLT definition will lead to dose interruption, dose modifications, and/or permanent discontinuation of study drug as defined in [Table 4.5.2-1](#) and in this section. The criteria presented in this section and [Table 4.5.2-1](#) for dose modifications and delays are meant as general guidelines.

- Subjects will continue to receive therapy as long as they have not had disease progression, meet discontinuation criteria, or drug-related AE requiring dose modification as described below.
- Dose modification, interruption, or delay may occur in the setting of lower grade AE and/or be more conservative than indicated in [Table 4.5.2-1](#) based on the clinical judgment of the investigator and in consultation with the BMS Medical Monitor.
- Dose reductions in this study are applicable to the administration of BMS-986148 and should be to the previous lower dose level. There are no dose reductions for nivolumab (applicable for Part 3).
- If several AEs of varying grade or severity occur simultaneously, the dose modification applied should be the greatest reduction of BMS-986148 applicable.
- Assessment of causality (chronology, confounding factors such as disease, concomitant medications, diagnostic tests, and previous experience with the agent) must be determined and documented by the investigator prior to dose modification.
- If the same  $\geq$  Grade 3 nonhematologic AE recurs despite a dose reduction, a second dose reduction versus discontinuation of the subject from further protocol therapy will be discussed and agreed upon by the BMS Medical Monitor and investigators.
- No more than 2 dose reductions of BMS-986148 will be allowed per subject. If a third dose reduction is required, the subject must discontinue study drug. Dose re-escalation after a dose reduction may occur in limited circumstances (such as a change in attribution of an AE) after discussion and agreement of the BMS Medical Monitor and investigators.
- Skipped BMS-986148 doses in Part 1B will not be administered within the same cycle.

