- For an AE requiring dose modification, study drugs should be interrupted to allow recovery from the AE. Re-initiation of study drug cannot occur until AE decreases to  $\leq$  Grade 1 or baseline assessment (See exception for Part 3 below in [Section 4.5.4](#)). In case of delayed recovery to  $\leq$  Grade 1 or baseline (except for alopecia) from treatment-related AEs that results in a delay of treatment for  $> 30$  days, the subject will not receive additional protocol-related therapy (applies to BMS-986148 monotherapy in Parts 1 and 2) and will still continue in follow-up periods unless discussed and agreed upon by the BMS Medical Monitor and investigators that it is in the best interest of the subject to receive additional therapy with BMS-986148 (for example, if the subject has demonstrated a response to therapy). For dose delay in Part 3, see below.
- For additional dose modifications pertinent to nivolumab (Part 3), see [Sections 4.5.3](#) through [4.5.5](#) below.
- During the DLT evaluation period, if a subject is dose reduced and experiences a DLT at the lower dose, this DLT will be attributed to the highest dose level administered.

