**Table 4.5.2-1: Dose Modifications**

Dose Modification Criteria for Drug-Related Adverse Events	BMS-986148 (Parts 1, 2, and 3) (Modification at Next Dose)
Grade 4 neutropenia lasting > 5 days	Decrease 1 level.
Grade 3 febrile neutropenia lasting > 48 hours	Decrease 1 level.
Grade 4 febrile neutropenia	Discontinue.
Grade 4 thrombocytopenia or ≥ Grade 3 thrombocytopenia with clinically significant bleeding	Decrease 1 level.
QTcF > 500 msec confirmed by at least 1 repeat ECG and at least 60 msec above baseline	Interrupt if needed to optimize electrolyte management; if persists after electrolyte optimization (including dose modification of BMS-986148, if necessary), discontinue.
Grade 1 Troponin I or T confirmed when repeated in 72 hours	Discontinue.
Grade 3 Troponin I or T	Discontinue.
AST or ALT > 5 times the institutional ULN that last ≥ 5 days or is symptomatic	Decrease 1 level.
≥ Grade 3 infusion-related reaction	See Section 3.4.1 .
≥ Grade 3 peripheral neuropathy	Discontinue.
≥ Grade 2 uveitis or eye pain or reduction in visual acuity a that improve to Grade 1 within 2 weeks of initiation of topical therapy	Interrupt dosing until improvement to Grade 1 or baseline and decrease 1 level.
≥ Grade 2 uveitis or eye pain or reduction in visual acuity a that does not respond to topical therapy and that does not improve to Grade 1 within 2 weeks of initiation of topical therapy	Discontinue.
≥ Grade 3 eye symptoms	After improvement to Grade 1 or baseline, additional therapy with BMS-986148 (decrease 1 level) may be considered after discussion and agreement by the BMS Medical Monitor and investigators that it is in the best interest of the subject (for example, if the subject has demonstrated a response to therapy).
≥ Grade 3 eye symptoms	Discontinue.

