Cardiac monitoring with echocardiogram at baseline, start of Cycle 3, then every 3 cycles, and EOT will be conducted during the Part 1 and 2 (Monotherapy treatment) . For subject in Part 3 combination treatment, an additional echocardiogram at the start of cycle 2 will be done. MUGA scan can be used for the assessment of LVEF at baseline. Echocardiograms done during treatment for the monitoring of pericardial effusion may be obtained more frequently if indicated. Troponin T or I will be monitored QW during the first cycle. Grade 1 elevation requires dose interruption of study drug and repeat assessment within 72 hours; BMS-986148 should be discontinued if Grade 1 Troponin T or I is confirmed when repeated assessment occurs. If persistent elevation, dose discontinuation should be considered at the discretion of the consulting cardiologist and discussion with the medical monitor. Grade 3 elevation of Troponin I or T requires discontinuation of study drug and prompt consultation and management with a cardiologist is recommended until it resolves.

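### Protocol Section 5.3 gives two inconsistent instructions for a Grade 1 troponin elevation confirmed on the 72-hour repeat: discontinue BMS-986148, or consider discontinuing it

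*Protocol*

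**What the plan says.** Protocol Section 5.3 sets out troponin handling in one short run of sentences. A Grade 1 elevation leads to dose interruption and a repeat within 72 hours. Then "BMS-986148 should be discontinued if Grade 1 Troponin T or I is confirmed when repeated assessment occurs". The sentence after that reads "If persistent elevation, dose discontinuation should be considered at the discretion of the consulting cardiologist and discussion with the medical monitor". Grade 3 follows in its own sentence, which requires discontinuation and recommends a cardiologist.

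Other parts of the protocol bear on the same event:

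- **Table 4.5.2-1**, headed as covering drug-related adverse events, has a row for "Grade 1 Troponin I or T confirmed when repeated in 72 hours". Its action is to discontinue, with no exception. The Grade 3 troponin row has the same action.
- **Section 3.5** lists reasons for which a subject must stop investigational product. One is "AE(s) requiring discontinuation as outlined in the Dose Modification section".
- **Section 4.5.2** says that its criteria "for dose modifications and delays are meant as general guidelines".
- **Section 5.3.1 and Tables 5.1-2, 5.1-4 and 5.1-6** schedule on-treatment troponin in Cycle 1 of Parts 1 and 3A only.

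**The concern.** A Grade 1 elevation found again on the repeat is, on a plain reading, a persistent elevation. For that result one sentence tells the site to stop BMS-986148, and the next tells it to consider stopping after taking advice. Two sites could act differently on the same laboratory value and each could cite Section 5.3.

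What is at stake is individual safety. Elevated troponin at screening is an exclusion criterion (Section 3.3.2), and one related Grade 3 pericardial effusion had already been reported at 1.6 mg/kg (Section 1.5.1). The protocol sets its troponin stop at the lowest grade, so the instruction at that grade should be clear.

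**Working it through.** The protocol gives no figure for this point, so the main check is a comparison of texts.

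**Step 1. Can the second sentence refer to something else?**

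- *Elevation continuing after the confirmed repeat.* BMS-986148 would already have been stopped under the preceding sentence, so nothing would remain to be considered for that drug.
- *Another grade.* The sentence names none. Grade 3 has its own mandatory sentence, and Table 4.5.2-1 has troponin rows only for Grades 1 and 3.
- *Nivolumab in Part 3.* The sentence names no drug, and the surrounding troponin text is not limited to Part 3. This reading is possible but not stated.

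**Step 2. Which instruction does the rest of the protocol support?** Table 4.5.2-1 says discontinue. Section 3.5 turns that into a must-stop by referring to the Dose Modification section. Both agree with the first sentence.

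**Step 3. Does a listed flexibility cover continued dosing?** Section 4.5.2 says "Dose re-escalation after a dose reduction may occur in limited circumstances", but that follows a reduction, not a discontinuation. It also allows further therapy by agreement after a delay of more than 30 days, which concerns slow recovery. Table 4.5.2-1 says, for an eye event, that "additional therapy with BMS-986148 (decrease 1 level) may be considered after discussion and agreement by the BMS Medical Monitor and investigators"; the table is broken in the text available, so the exact eye row is uncertain. The troponin rows carry nothing similar.

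**Step 4. Do the resumption provisions permit a restart?** No. Section 4.5.2 continues therapy only for subjects who do not meet discontinuation criteria. Section 4.5.3 limits resumption in Part 3 to subjects who do not meet the guidelines for permanent discontinuation.

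**Step 5. How many subjects could be involved?** Inputs: 0 elevations in 30 Part 1A subjects by 01 July 2016 (Section 1.5.1); about 24 subjects planned for Part 1B and 12 for Part 3A (Section 8.1); 179 to 204 monotherapy and 137 to 162 combination subjects planned (Synopsis).

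- Exact two-sided 95% upper bound for 0/30: 1 − 0.025^(1/30) = 0.1157, or 11.6%.
- Further planned subjects with scheduled testing: 24 + 12 = 36.
- Share of all planned subjects: 36/(179 + 137) = 36/316 = 11.4%, down to 36/(204 + 162) = 36/366 = 9.8%.
- Expected elevations of any kind at the upper bound: 36 × 0.1157 = 4.2.
- At assumed rates of 1% and 5%: 36 × 0.01 = 0.36 and 36 × 0.05 = 1.8.
- If 12 more subjects (an assumed number) were added at established dose levels: 48 × 0.1157 = 5.6.

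**The case against.** The strongest reply is that the operative rule is clear. The preceding sentence, Table 4.5.2-1 and Section 3.5 all point to stopping. The discretionary sentence is not worded as an exception and nowhere says that dosing may continue. A careful investigator who reads all three places would stop the drug. This stands, and it is why the point is small. It does not remove the inconsistency: Section 4.5.2 calls its own criteria general guidelines, and a site consulting Section 5.3 alone meets both sentences together.

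A second reply is that the preceding sentence stops only BMS-986148, so the next may concern nivolumab, which Section 4.5.3 manages separately. That would be coherent in Part 3A. The sentence does not say it, however, and troponin is also scheduled in Part 1, where there is no nivolumab.

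A reader might also infer something stronger: that the restart rules leave a route back to dosing. Section 4.5.2 says "Re-initiation of study drug cannot occur until AE decreases to" Grade 1 or below, or baseline, and a confirmed Grade 1 troponin is already at that level. Section 4.5.4 uses a similar threshold for Part 3. The documents do not support this inference. The threshold governs recovery after an interruption, not a row whose action is to discontinue, and the provisions in Step 4 exclude a subject who has met discontinuation criteria.

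**Conclusion.** The inconsistency is real and sits in two consecutive sentences of Section 5.3. The discretionary sentence is the one out of line with the rest of the protocol.

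Its size is small. About 4 expected elevations is an upper bound on elevations of any grade, confirmed or not. It does not forecast cases or count subjects who would be kept on drug because of this sentence, and the documents give no basis for a rate of misapplication. The bound assumes that all 30 Part 1A subjects were tested on treatment, that their rate carries over to Parts 1B and 3A, and that neither of those parts had enrolled by 01 July 2016. For Part 3A that follows from the Document History, where the amendment adding Part 3 is dated 21-Jul-2016. For Part 1B it is inferred, because Section 1.5.1 gives 30 both for subjects dosed on study and for subjects dosed in Part 1A. Unscheduled tests are not counted.

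No sample size, error rate, decision boundary or other statistical figure depends on this point. It should still be corrected, because it concerns a cardiac stopping rule and the correction is cheap.

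**What to change.** Replace the discretionary sentence in Section 5.3 with: *BMS-986148 is discontinued for a confirmed Grade 1 elevation (see Table 4.5.2-1); consultation with a cardiologist is recommended for further management.*

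Deleting the sentence outright would also remove the conflict, but it would lose the only mention in that paragraph of a cardiologist for an elevation below Grade 3.

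If the sponsor meant the discretion to apply to nivolumab in Part 3, the text should say so explicitly. Otherwise no nivolumab rule is needed. If the sponsor wants discretion for elevations judged unrelated to study drug, the preceding sentence must also be limited to drug-related elevations, as the table is; otherwise the conflict returns.

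The cost is one sentence in an amendment, with no change to visits, tests, sample size or analysis.
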